We will reach the population using social media ads on sites including Facebook, Tumblr, Instagram, Reddit, Twitter, and Spotify. Ad targeting within social media sites allows us to specify the age range and other socio-demographic characteristics of individuals who will see the ads based on the information they provide in their online profiles. We will develop ads that promote our target populations interest by including diverse images of youth (i.e., images of different ages, portraying diverse race/ethnicity), as well as using ad-targeting specific to socio-demographic characteristics (e.g., delivering Facebook/Instagram ads only to youth living based on their age, race/ethnicity and sex) and interests (e.g., TV shows with LGBT themes).

Social Media Influencers

We will pursue reaching out to social media influencers to assist in posting recruitment ads on their various platforms to their followers. This can be done through tweets, videos, or messages on Facebook/Instagram. These influencers will be those popular among LGBT youth. We will contact them in various ways including social media (twitter, facebook, etc...) or through sites such as Cameo. Messages recorded by influencers will be posted with recruitment ads and on current social media platforms used in the study. Instructions on what to include in the messages will be provided to the influencers prior to recording. An example of a recorded message would be: “What’s up, this is [name] and I just wanted to encourage young men to sign up for the research study called iReach. It’s a web app that can help young men with same sex attractions deal with topics relating to their sexuality during their adolescent years. It’s an awesome program, please look it up and tell them [name] sent you.”

Community Organizations and Universities

We will also seek approval from individual LGBT and youth-serving organizations to post advertisements on their websites and Facebook/Instagram pages. Physical recruitment materials will be developed and distributed among organizations that serve and support LGBTQ+ youth (such as homeless youth organizations, community LGBTQ+ centers, HIV resources, etc.). Likewise, we will seek opportunities to distribute recruitment materials at colleges and universities.

Community Events

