Materials will avoid identifying candidates as AMSM in the recruitment text to avoid unintended disclosure. Ads will link interested individuals to the study site where they may verify their eligibility, email the team, or locate a toll-free number if they want to talk to a team member about the study. AMSM will click on viewed social media advertisements and be taken to a homepage containing basic study information including a short description of study activities. The homepage will not identify the study as a site for MSM.

Screening: Interested individuals will be asked to consent to and complete an online screening survey. We will use this approach as one of our strategies for filtering fraudulent or duplicate entries (see Measures to protect against fraud and hacking below). Individuals who do not meet the eligibility criteria will be thanked for their interest and automatically routed to the Google home page. We will not indicate why they were ineligible to avoid unintentional disclosure and to protect against fraud. In order to meet recruitment sub-targets (e.g. by race/ethnicity), the eligibility screener programming will be modified to exclude groups as recruitment sub-targets are met. Participants who are part of these now-excluded groups and would otherwise be eligible to participate will be offered the opportunity to provide their contact information and be put on a study "waitlist." Individuals on this list may be re-contacted if recruitment targets are re-evaluated in the future. **Consent:** If they are screened eligible, they will be taken to the study consent form (a waiver of parental consent has been obtained for minor participants). To optimize AMSMs active understanding of the consent process, we also include a video with subtitles and key concepts from the consent form at the bottom of the video screen. The video will be followed by the full consent form, which AMSM will be prompted to read and then either consent to or reject participation. AMSM will also have the ability to download a complete version of the consent form. AMSM who do not consent will be taken to a screen thanking them for their interest (which will also include information on HIV testing). AMSM who consent to participate will be directed to continue through the registration process.

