We note several advantages and disadvantages of conducting online and mobile-based research and interventions. An advantage of online research is data validity; a growing number of studies indicate higher reporting of sexual risk and substance-using behaviors with computer-based surveys compared to mail, phone, and in-person surveys. However, compared to the gold standard (in-person interviewing), a limitation of online research like mail and phone surveys is the challenge of verifying a respondent's identity. Based on our prior work, we will use best practices to reduce the likelihood of online fraud by keeping compensation sufficiently low (i.e., balance incentives with the effort required from respondents) to reduce the chances of respondents participating solely to gain incentive payments, and verifying contact information using multiple verification methods, including email, cell phone, and mailing address. The validation, or verification, of participant contact information is the "gold standard" for fraud prevention. This process is commonly used in online research and will prevent multiple submissions as well as help ensure that the intended participant fills out the responses. We will verify participant information using two forms of personal information, including their mobile phone, to ensure that the participant's mobile phone number is unique in the study database. We will also run duplicate detection software continually (i.e., respondent creates a fake user profile to gain incentives) until recruitment is complete and all subjects are verified. Responses from the screening survey will be checked against responses in the baseline survey to ensure consistency, and IP addresses, email addresses, and phone numbers will be reviewed to check for multiple registrations. Proxy IP addresses will be flagged for further scrutiny, and reviews of the baseline survey data will be conducted to check for suspicious response patterns and realistic completion times. Within 48 hours after verifying the baseline survey, participants will be sent an email confirmation. Within 24-48 hours after verifying their email, participants will receive their login credentials for the iReach WebApp and subsequently their incentive payment for completion of the baseline survey. Prior to receiving the login credentials, participants are assigned into a 1:1 ratio using a stratified randomization by race and region into the Intervention or Attention-Control condition. Screener and baseline data will be used by iReach to inform personalized, tailored content for AMSM assigned to the intervention condition.

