participation of the respondent, such that the respondent is aware of the nature of the questions to be included in the surveys. The study website will provide these details in full, during the consent process, and once the participant has created their password protected profile they will be able to access full information on the expectations of participation and the types of questions they will be asked. Informed consent documents will inform research participants of the need to keep answers to questions confidential. Participants will have the option to refuse to answer or skip any questions on the surveys that they are uncomfortable answering. 2) Psychological distress is a potential risk to AMSM during the completion of the surveys, reading the intervention content and during the teleconference counseling. We will provide AMSM with information to allow them to contact crisis services at the National Runaway Safeline at any time if they experience psychological distress, and the ability to contact the study team if they experience any adverse effects related to participation in the study. If psychological distress is apparent during a tele-conference, our licensed clinicians will be available to talk with the participant. In addition, we will refer crisis cases to the National Runaway Safeline which is available 24 hours a day, 7 days a week. In consultations with the leadership of the National Runaway Safeline, it was determined that crisis line staff would not need study-specific training in order to provide quality crisis support services to study participants, and actually might complicate the process. National Runaway Safeline staff are trained in providing crisis counseling to this age group, including sexual and gender minority youth. Research staff will receive training in crisis assessment and management procedures in the unlikely event that participants reveal suicidal and/or homicidal ideation, or child physical/sexual abuse. We will use established protocols from our prior studies conducted with youth and MSM for research staff to guide them in responding to crisis or harm situations, including attempting to contact the participant to assess risk level and provide appropriate follow-up (e.g., crisis hotline, safety check, suicide hotline). We will notify participants when we must engage in mandatory reporting during the consent process and when the participant decides to share a reportable event with study staff. 3) Unintended disclosure is also a potential risk. Given parents potential to monitor what apps their children have downloaded on their phones, we opted to keep iReach as a mobile-friendly WebApp. As a result, only individuals who know the URL can access the site. Participants will be instructed at different moments during the study (e.g., screening, baseline, followup) of steps they can take to further protect their privacy (e.g., clear browser history; avoid saving username/password in browser; logging out every time; using the app in private; using a screen lock on their phones, if parents allow). In addition, to limit inadvertent disclosure of their participation in the study to parents or others, we will suggest that youth create strong passwords (mix of upper/lower case letters, numbers, or symbols) on their iReach and personal e-mail accounts. Further, youth will choose how they wish to be contacted by the study staff (e.g., email, text message, private message on Facebook), and none of these exchanges will include sensitive information about HIV/STI, MSM, or anything that may reveal their participation in a study or answers to any of the questions answered in the surveys. Participants will be asked to provide at least two forms of contact information. Because participants are providing these pieces of identifiable information, there is a possibility that their participation in a research study could be disclosed in the following ways: (1) if someone other than the participant sees the intervention content; (2) if someone besides the participant reads the email sent with the link to the follow-up survey in which participants will enter their results; or (3) if someone besides the participant sees the study text messages, or online surveys on participants computer, tablet or phone. The risk of disclosure of participation in a research study through receiving study related emails, receiving text messages, interacting with the online surveys or with the study application on the participants cell phone will be minimized in the following ways: (1) participants must always log-in to re-enter the site after periods of inactivity as a fail-safe to avoid unintended disclosure; (2) emails with a link to the study follow-up surveys will not make any reference to the nature of the survey; for online surveys, participants will be required to login to the study website with the username and password that they created as part of the registration process before beginning the baseline survey; (3) participants will be encouraged to delete any text messages received as part of the study to protect them from an unauthorized individual viewing the messages, and to interact with the study application when in private (e.g., screen lock, complete when alone). Participants will be notified of these risks in the consent process. 4) One potential challenge is the security and confidentiality of VSee. Unlike other video-chat platforms (e.g. Skype), VSee is HIPAA-compliant and will be used for the peer mentoring sessions. Participants will have the option to use VSee in several formats: face-to-face video chat, video chat in which they can see the peer mentor but the peer mentor cannot see them, audio chat only, or a text based conversation. The consent form will include a full description of VSee, their options for using VSee, and will also make it clear that they can opt to have as many or few VSee sessions they wish (after the introductory session). Participants will request a VSee session through the iReach WebApp: when requesting a VSee session participants will be able to indicate the format they would like the session to take (e.g. face to face or audio only). VSee is compatible on PCs, tablets and smartphones. VSee includes the following functions to protect users: - End-to-end encryption without a man-in-the-middle listener. In WebEx, Vidyo, Tandberg, and Polycom architectures, your media is sent to a server (also called a video relay or MCU). Although encryption is applied from the users computer to these servers, the servers still have full access to the users media. In contrast, VSee uses end-to-end encryption where no server, including VSee servers, has the decryption key. VSee uses public/private RSA keys to exchange a 256-bit AES session key with the property that only the endpoints have the AES session key. VSee uses FIPS 140-2 certified 256-bit AES encryption. - One port. H.323 systems not only require many ports, but they require dynamic ports. This means if you want to use H.323 across your firewall, you are essentially opening your network to attackers on many ports. VSee, on the other hand, uses a single port for call signaling and media. The VSee protocol is structured so that only the outgoing port needs to be open because return traffic is always structured as responses to outgoing traffic. This allows administrators to set a policy where if users

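### The example influencer message ties the name iReach to same-sex attraction, which is inconsistent with the protocol's own rule on recruitment text

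*Protocol*

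**What the plan says.** All references are to the protocol; the SAP text does not deal with recruitment wording.

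- **Subject Recruitment and Screening, Social Media Influencers.** The study will approach influencers popular with LGBT youth, tell them what to include, and publish their recordings alongside the ads and on the study's own channels. The model text is introduced with "An example of a recorded message would be". In it the influencer wants to "encourage young men to sign up for the research study called iReach" and describes iReach as "a web app that can help young men with same sex attractions deal with topics relating to their sexuality".
- **Same section, later paragraph on recruitment materials.** "Materials will avoid identifying candidates as AMSM in the recruitment text to avoid unintended disclosure". The sentence appears again in Study Procedures under Strategies to Ensure Sample Diversity. Neither place exempts influencer messages.
- **Same section, on the page the ads lead to.** "The homepage will not identify the study as a site for MSM".
- **Risk/Benefit Assessment, Risks, item 3.** Unintended disclosure is a named risk with several controls. One is that study contacts stay neutral: "none of these exchanges will include sensitive information about HIV/STI, MSM, or anything that may reveal their participation in a study".
- **Subject Recruitment and Screening, on enrolment.** After verification, "participants will receive their login credentials for the iReach WebApp". Compensation and Incentivization confirms that these credentials go out by e-mail.

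**The concern.** The example states publicly the attribute that the recruitment text is meant to leave out, and attaches it to the name shared by the study and the WebApp. A name that has been publicly explained in this way is no longer neutral to someone who knows the explanation.

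The participants are 13 to 18 years old. The Children and Adolescents section of Informed Consent says they may not have told their parents about their attractions, and it cites rejection and abuse by family members as possible consequences of disclosure. Because the association attaches to the name, it could also reach a participant who enrolled through a neutral ad and never saw the recording.

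**Working it through.** No arithmetic applies to the contradiction itself, so the check is a comparison of texts.

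1. **Is the influencer message covered by the rule?** It asks people to sign up, appears in the recruitment section, and is published with the ads. The rule speaks of materials and recruitment text in general. The example is a recording, but the protocol also foresees tweets and written messages from influencers, and the rule's stated purpose applies equally to speech. It is covered.

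2. **Does the message state the withheld attribute?** The rule withholds AMSM status. The message states maleness, adolescence and same-sex attraction. Same-sex attraction or behaviour is inclusion criterion 4. The attribute is stated.

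3. **Does it affect the homepage rule?** The message does not change the homepage, so that rule is not broken. But a viewer who arrives by way of the recording has already been told what the homepage leaves unsaid. The rule is undercut.

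4. **By what route could a participant be exposed?** Two conditions must both hold: an observer sees the name iReach linked to the participant, and the observer knows the message or finds it.
   - The credentials e-mail is the most concrete candidate for the first condition, but the protocol does not give its wording.
   - Subject Follow-up quotes a reminder from a prior study that contained that study's app name (iCON). Nothing says iReach reminders do the same.
   - No section says that the URL, browser tab or sender name shows iReach.
   - The route is therefore possible, not established.

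5. **Which controls remain?** Item 3 of Risks also relies on a WebApp instead of a downloaded app, access only for those who know the URL, passwords, repeat log-in after inactivity, contact modes chosen by the participant, and advice on browser history and screen locks. A public message leaves these in place. Log-in, however, protects the content and does not prevent an inference from seeing the name.

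6. **Can the exposure be counted?** Study Instruments gives 5 surveys (intervention) or 6 (control), including baseline, which comes before the credentials are sent. The later surveys number 5 − 1 = 4 or 6 − 1 = 5. These cannot be turned into exposures, because nothing says that survey notices carry the name. No disclosure rate is given either.

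**The case against.** The strongest defence has four parts.

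- **It is only an example.** This is correct. The text is not a mandated script, the influencer plan is tentative, and nothing shows that this wording was recorded or posted. But it is the only model message in the protocol, and the study controls the instructions given to influencers.
- **It describes a group and identifies no individual.** On the literal words this is arguable. But general recruitment text never names individuals, so on this reading the rule would forbid almost nothing. The stated purpose and the neutral homepage both point to the wider reading.
- **Other controls still work, and participants are told of the disclosure risks at consent.** This stands. It limits the consequence but does not remove the inconsistency.
- **The association would exist anyway.** Influencers are chosen for their following among LGBT youth, and materials go to LGBTQ+ organisations and Pride festivals. This also stands: rewording the message reduces the association and cannot abolish it.

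**Conclusion.** The example influencer message is inconsistent with the recruitment-text rule, which the protocol states twice, and it undercuts the neutral-homepage rule. The passages must be reconciled. The consequence is that one of several stated disclosure controls is weakened. Its size cannot be computed from the documents, and sample size, power and analysis are unaffected. The conclusion assumes that the rule covers influencer messages and is read by its purpose. The disclosure route further assumes that some study contact shows the name.

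A reader might infer more, but the documents do not support it:

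- **That the message defeats the main control on disclosure.** No section ranks the recruitment rule as the main one, and the controls in Risks still operate.
- **That all 600 participants are identified by every study notice.** This requires each notice to show the name, which is nowhere stated, and Risks promises neutral contacts.
- **That the parental waiver loses its basis.** The waiver rests on three grounds (mature-minor capacity, possible family reactions, practicability), and none is tied to recruitment wording.
- **That the sample will shift towards youth who are already out.** This is conceivable, but nothing in the documents bears on it.

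**What to change.** - Replace the example with wording that does not pair the study name with same-sex attraction or sexuality, for instance a research study for young men about life skills, with a link. Dropping the name but keeping the description would not be enough, because the text would still state what the recruitment rule withholds.
- State the same limit in the instructions to influencers, so that they do not add the description themselves.
- If any recording that pairs the two has been posted, replace it.

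The cost is a wording change and an IRB modification of recruitment material. A less specific message may draw more clicks from ineligible people, which the eligibility screener already filters.
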